#### 8.5 DATA SOURCES

This study will be conducted using the HIRD, a large administrative healthcare database maintained by HealthCore for use in health outcomes and pharmacoepidemiologic research. The HIRD includes longitudinal medical and pharmacy claims data from health plan

members across the United States (US). Member enrollment, medical care (professional and facility claims), outpatient prescription drug use, outpatient laboratory test result data, and health care utilization may be tracked for health plan members in the database dating back to January 2006, and with diagnoses recorded in International Classification of Disease, Version 10 (ICD-10) since October, 2015. Laboratory result data are additionally available for those tests that have been performed using two large, national reference laboratories (Quest and LabCorp) [R14-4278]. The database has been used for the study of numerous diseases, including studies of COPD [R19-2324; R19-2321; R19-2323; R19-2322; P15-11025; P14-12233].

#### **8.6 BIAS**

Several potential biases are inherent to any observational study in the HIRD. In the absence of randomization, confounding by indication could be an issue. Controlling by propensity score should limit this bias, but can control only for measured covariates and may produce estimates that are impacted by residual confounding. This is of particular importance in the case of lifestyle factors that are less critical to insurance billing and thus poorly captured in claims data. Quantitative bias analyses can formally describe the extent to which these issues are present, but bias analysis parameters are informed by literature and clinical expert opinion. As such, the accuracy of bias corrected analyses is limited by the accuracy of the assumptions that inform them.

Second, there is the possibility of information bias due to misclassification of the outcomes or exposure or missing data, especially, differential missingness of some data (e.g. eosinophils, which may only be measured in sicker patients). The prescriptions dispensed by a pharmacy but not taken by patients could lead to misclassification of exposure. Pharmacy dispensing data does bring us one step closer to patient use than physician prescribing given that the patient has taken the effort to obtain the medication as instructed, however, information such as indication can only be inferred based on diagnostic patterns.

#### 8.7 STUDY SIZE

Preliminary counts of FDC Tio+Olo and ICS/LABA users in the HIRD are shown here:

	Tio+Olo		ICS/LABA	
	N	%	N	%
New users	8,233	100.0	341,352	100.0
At least 12 months of pre-index eligibility	6,263	76.1	187,093	54.8
Age 40+	6,126	97.8	136,310	72.9
At least 1 diagnosis of COPD	5,469	89.3	53,432	39.2
At least 1 eosinophil % result prior to the index date	2,207	40.4	19,407	36.3
Eosinophil result (N, % of those with				
a result)				
0-2%	1,059	48.0	8,907	45.9
2-4%	745	33.8	6,698	34.5

D 1	' C	Y 11 1 Y 1	0 177	01. 011. 1
Proprietary confidential	information © 2020 Boehring	ger Ingelheim International	GmbH or one or more of	of its affiliated companies

4%+	403	18.3	3,802	19.6
Eosinophil result, patients with low				
exacerbation history(0 inpatient and				
0-1 outpatient events at baseline, N,				
%)				
<300 cells/uL	1,381	30.0	12,351	27.1
≥300 cells/uL	481	10.5	4,437	9.7
Unknown	2,739	59.5	28,733	63.1
Eosinophil result, patients with high				
exacerbation history (1+ inpatient or				
2+ outpatient events at baseline, N,				
%)				
<300 cells/uL	226	26.0	1,820	23.0
≥300 cells/uL	105	12.1	670	8.5
Unknown	537	61.9	5,421	68.5

In a recent analysis of the risk of exacerbations based on Clinical Practice Research Datalink (CPRD), a total of 2,000 patients per cohort detected a 15% difference in risk of a first exacerbation (hazard ratio 0.85) with over 90% power. As such, overall analyses are expected to have adequate power. Analyses that are stratified based on the presence of claims-based indicators of exacerbation and/or limited to individuals with specific eosinophils levels will be more limited. Given low expected sample size, stratification by eosinophil results within individuals with exacerbations at baseline will not be performed.

#### 8.8 DATA MANAGEMENT

All statistical analysis for the study will be conducted using SAS version 9.4 or higher (SAS Institute, Cary, NC). All sensitive data pertaining to the study will be stored on secured servers with access only permitted by approved study team members.

A number of Information Security policies are enforced, audited, and in place at HealthCore, including complex password requirements and encryption systems. Security mechanisms and policies are in place HealthCore's facilities are standard corporate office space. Office space is segregated and managed by monitored electronic access. HealthCore areas which contain project and study-related documents are only access by HealthCore associates or contract personnel. All non-HealthCore associates must be accompanied by an associate at all times in order to enter these areas. All study related files are kept in locked cabinets and work areas. There are no visible labels or client listings viewable by any visitor or passerby. All passwords and user authentication mechanisms are forced changed at regular intervals and there is automatic locking of workstations after a short period of time (< 15 minutes).

Data Center space is permitted on an as required basis and monitored by electronic access. HealthCore maintains a cumulative record that indicates, for any point in time, the names of authorized personnel, their titles, and a description of their access privileges to the Data Center. Data access is restricted, monitored, logged, and audited. HealthCore's computer

Proprietary confidential information © 2020 Boehringer Ingelheim International GmbH or one or more of its affiliated companies

networks have been designed to separate patient or physician identified data from deidentified or masked data. Network security, firewalls, and password permissions control which HealthCore personnel have access to patient or physician identifiers. Unless the study protocol calls for patient or physician authorization or a waiver of authorization as granted by an IRB, no research analyst will have access to patient or physician identifiers within HealthCore's computer systems. All research analysis databases have been de-identified. HealthCore's Data Center is also physically secured by a controlled access facility, with only authorized personnel having access to network servers, tape libraries and other media that contains patient identifiers.

Research analysis files used by HealthCore do not contain patient or physician identifiers unless necessary to perform such research; if such is the case, access will be made after receipt of the patient's or physician's authorization or IRB waiver of such authorization has been granted. It is also HealthCore policy to provide for secure storage of study materials, including data, reports, and other files after the study is completed, with a destroy date assigned based on study requirements. HealthCore reviews data requirements for each study to assure that only the minimum of patient or physician information is obtained to answer the research question(s). For those studies where direct patient identifiers are needed for additional data collection such as medical chart abstracts, access to information will be limited to the greatest possible extent within the research team. Both structural and contractual safeguards reinforce policies to minimize the risk of breaching patient or physician privacy. The structural safeguards include a clearly defined data flow process. This process minimizes the risk of individual identifiers being improperly used or disclosed. The contractual safeguards include contractual binding to confidentiality of individuals involved in the research.

Stratified analyses will use the same approach. Because not all individuals will have available laboratory result data available, fine stratification and reweighting by propensity score will be repeated within the subset of the cohort with available results to create weighted populations suitable for these stratified analyses. Potential effect modification by B-Eosinophils and/or exacerbation history will be studied by comparing models with and without interaction terms and through qualitative consideration of differences in stratum-specific estimates.

The analysis of the secondary objectives related to the risk of pneumonia, treatment escalation, and an adverse outcome will use a Cox proportional hazard regression model with an as-treated approach, similar to that of the primary analysis.

In terms of healthcare utilization, we will present continuous and categorical variables using standard descriptive statistics to describe total visits and total costs related to inpatient, outpatient, office visit, and emergency care as well as total pharmacy dispensings, distinct medications used, and pharmacy costs. Utilization and costs will be stratified to facilitate comparison between Tio+Olo and LABA/ICS, and presented by individual setting and as a composite. All-cause and COPD-specific data will be shown.

Proprietary confidential information © 2020 Boehringer Ingelheim International GmbH or one or more of its affiliated companies

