19 February 2020	1237-0093	1.0	NA
© 2020 Boehringer Ingell This document may not - in	heim International GmbH n full or in part - be passed on,	confidential information or one or more of its affiliated comp reproduced, published or otherwise used with	thout prior written permission
The primary objective is to compare the effectiveness of maintenance therapy initiation with the combination treatment Tiotropium and Olodaterol (Olo+Tio) compared with LABA/ICS combination in COPD as the time to the first COPD exacerbation.  Secondary objectives are to compare patients treated with Tio+Olo and patients treated with LABA/ ICS combination: (1) Time to community acquired pneumonia, (2) time to escalation to triple therapy (3) time to an adverse outcome including exacerbation, escalation to triple therapy, or pneumonia, and (4) healthcare utilization outcomes and an analysis of all-cause and COPD-specific cost overall and by care setting.  Additionally, the study will investigate the effect modification of circulating eosinophil levels and exacerbation history on the safety and effectiveness of Tio+Olo compared with any LABA/ICS. Analyses will be repeated in subgroups of patients under high or low risk of exacerbation based on previous history of exacerbations in the year preceding cohort entry (with exacerbation history defined as either 1+ hospitalization or 2+ exacerbations in emergency department or outpatients settings [R05-1384]), as well as based on circulating eosinophils (cut-off: B-Eos 300cells/uL [P18-09975]) overall and among those without a history of exacerbation.			
Study design:	A incident new-user cohort design will be used, with confounding controlled via fine stratification and reweighting of time-conditional propensity scores		

Proprietary confidential information © 2020 Boehringer Ingelheim International GmbH or one or more of its affiliated companies

Name of company:			
Boehringer Ingelheim			
Name of product: Stiolto/Spiolto			Boehringer Ingelheim
Name of active ingre Tiotropium bromide +			
Protocol date:	Study number:	Version/Revision:	Version/Revision date:
19 February 2020	1237-0093	1.0	NA
© 2020 Boehringer Ingell This document may not - in	heim International GmbH n full or in part - be passed on,	confidential information or one or more of its affiliated compreproduced, published or otherwise used w	ithout prior written permission

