Although, a recent population-based observational study showed no difference in exacerbation risk for COPD patients with B-Eosinophils below 300 cells/uL) if treated either with LAMA or LABA/ICS [P18-09975], this data have yet to be confirmed in population based studies in real world conditions. Given high-cost adverse events associated with long-term use of ICS and inconsistent evidence concerning whether there is a clinically relevant benefit of ICS combination therapy in terms of disease control, it is important to assess differences between subsets of COPD patients in terms of the effectiveness and cost of LABA/ICS combination therapies versus other non-ICS options, such as Tiotropium+Olodaterol (Tio+Olo).

The proposed study will investigate the comparative effectiveness of Tio+Olo vs any LABA /ICS combination in COPD, describe differences in healthcare utilization, and compare cost effectiveness. Whether associations with time to exacerbation, community acquired pneumonia, escalation to triple therapy, and adverse outcome are modified by exacerbation risk (measured based on individual history and eosinophil levels) will also be assessed.

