#### Exploratory objective:

To assess differences between Tio+Olo vs any LABA/ICS combination in all-cause and COPD-specific healthcare utilization and cost overall and by care setting

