#### Exclusion Criteria:

- 1. To increase the likelihood of a true diagnosis of COPD, we will exclude:
  - a) All patients less than 40 years of age on the index date, and
  - b) All patients with a diagnosis of asthma in the year prior to the index date
- 2. To limit the population to those without severe lung compromise outside of COPD, we will exclude individuals with lung cancer, interstitial lung disease, or lung transplant identified at any time prior to the index date
- 3. To restrict the cohort to new users of Tio+Olo or LABA/ICS, we will exclude any individual with use of either Tio+Olo, LABA/ICS, or LABA/LAMA/ICS

combination therapy in free or fixed form for at least one year prior to the index date.

Outpatient laboratory data is available for a subset of patients. Some analyses will be further restricted to the subset of the population with at least one laboratory result showing circulating eosinophil levels within six months before the index date.

Individuals in the study cohort will be followed from the index date until the earliest of the date of a switch in treatment, addition of either an ICS for the Tio+Olo group or of LAMA to the LABA/ICS group, discontinuation of COPD treatment, the end of the study period, or the end of continuous health plan eligibility. Main analyses will be further limited to the first year after cohort entry, with sensitivity analyses considering all available data.

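### Healthcare use and cost are compared as descriptive totals by arm, with no visible person-time denominator, observation window or statement that the propensity weights apply

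*Combined protocol and SAP*

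**What the plan says.** Section 8.9.1 (Main analysis) gives healthcare use and cost one short paragraph. The method is standard descriptive statistics, used to "describe total visits and total costs related to inpatient, outpatient, office visit, and emergency care", together with total dispensings, distinct medications and pharmacy costs. On how the arms are compared it says: "Utilization and costs will be stratified to facilitate comparison between Tio+Olo and LABA/ICS". Results appear by setting and combined, all-cause and COPD-specific.

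The purpose is comparative. The exploratory objective in Section 7 reads "To assess differences between Tio+Olo vs any LABA/ICS combination in all-cause and COPD-specific healthcare utilization and cost overall and by care setting". The abstract places the same item among the secondary objectives, as "healthcare utilization outcomes and an analysis of all-cause and COPD-specific cost overall and by care setting". Section 6 goes further and says the study will "describe differences in healthcare utilization, and compare cost effectiveness".

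Follow-up is defined for the cohort in Section 8.3, under the exclusion criteria: "Individuals in the study cohort will be followed from the index date until the earliest of the date of a switch in treatment", or addition of an ICS (Tio+Olo arm) or a LAMA (LABA/ICS arm), discontinuation, study end or end of plan eligibility. Main analyses are capped at one year. Section 8.4.1 allows a 15-day gap before discontinuation is declared.

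On confounding, Section 8.9.1 says in general terms that fine stratification and reweighting of the propensity score will be used. It does not list the outcomes or tables this covers.

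**The concern.** A total is rate multiplied by time. The only follow-up definition in the visible text stops at patient-specific treatment events. One of these, escalation to triple therapy, is itself a secondary outcome on which the arms may differ. An arm that stays on treatment longer collects more visits, dispensings and cost at the same monthly rate. An arm that escalates sooner stops accruing cost sooner and can look cheaper for that reason alone.

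The utilisation paragraph also does not say whether its tables come from the crude or the weighted population. A programmer could follow it as written and produce unweighted totals with no denominator and no interval. Section 6 names cost effectiveness as something to be compared, and the abstract's intended audience includes payers. At stake is a published cost difference that reflects time observed or case mix rather than treatment.

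**Working it through.** **Plan's own figure.** There is none to reproduce. The documents give no expected use, cost, persistence or mean follow-up by arm. The power statement in Section 8.7 concerns first exacerbation only.

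**Step 1: effect of unequal follow-up.** Assumptions (not from the documents): the same monthly cost *c* in both arms, a constant monthly rate *h* of ending treatment, and the plan's cap of 12 months.

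- Mean follow-up in months: m(h) = (1 − exp(−12h)) / h
- m(0.10) = (1 − 0.301)/0.10 = 6.99
- m(0.125) = (1 − 0.223)/0.125 = 6.21
- m(0.15) = (1 − 0.165)/0.15 = 5.56
- m(0.20) = (1 − 0.091)/0.20 = 4.55

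Mean total cost per patient is c × m(h), so *c* cancels and the crude ratio is m(h, Tio+Olo) / m(h, LABA/ICS):

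| Assumed h, Tio+Olo | Assumed h, LABA/ICS | Crude ratio of totals | Ratio per person-month |
|---|---|---|---|
| 0.10 | 0.10 | 1.00 | 1.00 |
| 0.10 | 0.125 | 1.12 | 1.00 |
| 0.10 | 0.15 | 1.26 | 1.00 |
| 0.10 | 0.20 | 1.54 | 1.00 |
| 0.15 | 0.10 | 0.80 | 1.00 |
| 0.20 | 0.10 | 0.65 | 1.00 |

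The same formula with yearly rates, 365 × (1 − exp(−h))/h, gives 189, 158 and 134 days at 1.5, 2.0 and 2.5 per year. The ratios are 1.20 (1.5 vs 2.0), 1.18 (2.0 vs 2.5) and 1.41 (1.5 vs 2.5); swapping the arms inverts them.

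Variation between patients is not enough on its own. The arms separate only if mean follow-up differs by arm.

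**Step 2: what the documents show on case mix.** High exacerbation history is the only severity measure tabulated by arm (Section 8.7). The preliminary counts there do not list the asthma and other lung-disease exclusions as steps.

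- Tio+Olo: 226 + 105 + 537 = 868 of 5,469 = 15.9%
- LABA/ICS: 1,820 + 670 + 5,421 = 7,911 of 53,432 = 14.8%
- Standardized difference: (0.1587 − 0.1481) / √[(0.1587 × 0.8413 + 0.1481 × 0.8519)/2] = 0.03, below the plan's 0.10 limit

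If such patients cost *r* times as much as others (assumed), the crude cost ratio from this imbalance alone is (1 + 0.1587(r − 1)) / (1 + 0.1481(r − 1)). That is 1.009, 1.016 and 1.027 for r = 2, 3 and 5. Other confounders are not tabulated by arm, so this does not bound confounding.

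**Step 3: do the weights cover these tables?** For the stratified analyses and for pneumonia, escalation and the combined adverse outcome, Section 8.9.1 carries the primary approach over explicitly. The utilisation paragraph has no such sentence, and it uses the same descriptive label as the baseline tables. On the other side, the reweighting sentence is general, and the primary Cox paragraph does not mention weights either. The text leaves the question open.

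**The case against.** The strongest reply is that much of the worry is inferred from silence. A reader might infer that the plan chooses unweighted, as-treated totals. The documents do not support that:

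- No sentence calls the totals unweighted. The general reweighting statement could cover every comparison of the arms.
- Section 8.9.1 attaches the as-treated label to the Cox models. For utilisation, unequal windows are a reasonable reading of Section 8.3, but they are not stated for this analysis.
- Some text cannot be seen. Section 8.4.1 cites a Section 8.9.2 and Annex 3.3 cites a Section 8.4.3; neither is available, and some text between Sections 8.4.2.2 and 8.4.4 was removed. Definitions may sit there.

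A reader might also infer that confounding adds to the follow-up effect. It could equally offset it, and the one severity measure available shows little crude imbalance. Finally, Section 7 labels the objective exploratory, which limits how much formality is owed.

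These points stand, and they reduce both the claim and the confidence. They do not remove the gap. The stated method is still totals by arm, offered for comparison, and the only visible follow-up rule stops at treatment events. The exploratory label helps less than it might, because the abstract calls the same objective secondary.

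**Conclusion.** The point holds as a weakness in the stated method, with moderate confidence. On the visible text, use and cost are compared through descriptive totals without a denominator, a window or a statement on weighting, so the result is open to differences in observation time and case mix. With no true difference, the crude ratio could lie anywhere from about 0.65 to 1.54 under assumed end-of-treatment rates of 0.10 to 0.20 per month. It is 1.00 if mean follow-up is equal. This range illustrates sensitivity and does not estimate the bias in this study. It rests on constant stopping rates, identical monthly cost and the one-year cap. The size and direction of confounding cannot be determined from the documents. The change should be made because it is cheap and gives a better comparison, but the primary analysis does not depend on it.

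**What to change.** 1. State the observation window for use and cost, and how follow-up shorter than the window is handled.
2. Make visit rates and mean cost per person-month, in the fine-stratification weighted population, the main comparison. Give robust or bootstrap 95% confidence intervals for the Tio+Olo minus LABA/ICS difference.
3. Keep crude totals as a secondary table, shown with mean follow-up by arm.
4. Give the objective one status: secondary (abstract) or exploratory (Section 7).
5. Remove the cost-effectiveness comparison from the abstract and Section 6 unless such an analysis is specified.

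The cost is a few sentences, a little code and one more table; the weights and follow-up times are already needed for the Cox analyses. Cost per person-month is slightly less intuitive than a total. It also does not remove informative censoring: if patients escalate or switch because they are worsening, the costs that follow are still lost. Either state this as a limitation, or add a sensitivity analysis over a fixed window that continues through treatment changes while the patient remains enrolled.

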#### 8.10 QUALITY CONTROL

HealthCore operates observational research studies with the goal that the services provided to our clients are of high quality. To support this imperative we believe it is critical 1) to have dedicated training and quality resources and 2) that all talking points and major processes to be implemented with the study be approved by Boehringer Ingelheim in advance.

HealthCore's quality control program is centralized within the Regulatory Compliance Office. The Regulatory Compliance Office Manager is responsible for quality control and reports directly to the Vice President of Operations of HealthCore on all quality matters. HealthCore's quality system is organized around the Quality Manual, the quality checks within the project life cycle, and Standard Operating Procedures (SOPs). HealthCore has procedures for retention of protected health information (PHI) and project data. The study will be tracked at various levels to help ensure that all aspects including project delivery, infrastructure, quality processes, resource management, and financial issues are addressed. To help ensure the highest level of quality on every project, HealthCore has established several layers of quality assurance throughout the project lifecycle.

Role Based Control Checks: Each member of the team is responsible to perform thorough quality control checks on their work. In addition, the PI and Research Project Manager are also accountable for quality of all deliverables.

Quality Check Points: Centralized "checkpoints" have been implemented during the data management cycle to help ensure accurate translation of programming requests.

Quality Assurance Standards: Standard review procedures have been developed and are applied throughout the project lifecycle.

Automation: HealthCore has developed standard definitions of many variables and disease states and developed programs to apply these standards as needed on projects. These standards help ensure consistency, repeatability and accuracy for each project.

